6.1 Surgery

6.1.1 Breast-conserving surgery

> Skin incision

The skin incision must be suited to the size and the location of the tumor to allow for exeresis in one piece. It must also allow for the insertion of the localizer necessary for irradiation.

> Tumorectomy:

The gland exeresis aims to obtain complete resection of the tumor, centered by pre-operative localization, with safety margins.

Orientation of the specimen and any other resections

The surgeon must give the pathologist the oriented operative specimen and with stained margins as per the current recommendations. An extemporaneous measurement of the gland exeresis margins will always be carried out per-operatively. The tumor must be resected with a minimum gland margin of 2 mm.

> Axillary node dissection must preferably be of the sentinel lymph node type.

PROT ID: 2009/OBS-01

NCT : NCT04414202

Date : 15 Dec 2019

6.2 INTRA-OPERATIVE RADIOTHERAPY

6.2.1 Technique

Per-operative irradiation must be localized precisely on the tumor bed. The gland resection areas of the

tumorectomy site are mobilized for this, brought closer together and sutured by the surgeon. A circular

localizer is then placed opposite the excision site and fixed to the table using a jointed metal device in

order to avoid any mobilization. Its diameter (between 4 and 6 cm) is chosen based on the tumor

diameter.

The patient is then transferred under the dedicated linear accelerator located inside the surgical block.

This localizer is then positioned in perfect alignment with the targeting device of the accelerator.

Anesthesia monitoring of the patient is ensured during the transfer and during irradiation using several

fixed and mobile monitors. The interval between surgery and per-operative radiotherapy is 30 to 35

minutes.

6.2.2 Per-operative irradiation

The choice of electron beam energy is decided by the radiotherapist based on the tumor diameter and

the thickness of the area to be treated, assessed jointly with the surgeon. An energy of 6 to 13 MeV is

usually used.

The dose delivered to the tumor bed is 21 Gy, which is calculated based on the isodose of 90%.

6.2.3 Remodeling and clips

After the intra-operative radiotherapy, clips will always be left in place in the tumor bed in order to

facilitate later follow-up of the surgical area.

The surgeon will carry out breast remodeling in order to optimize the later final cosmetic result.

6.3 Anatomical pathology analysis

The operative and sentinel lymph node specimens are analyzed as per the conventional recommended

procedures.

The limits are considered negative if there is a safety margin of at least 2mm between the tumour and

the resection margin marked with ink (Fisher 1994).6.3 Additional local treatments

6.4 Conduct of the study

During the consultation with the surgeon, intra-operative partial irradiation is offered to patients who

meet the recommended criteria. The patient is invited to participate in the observational study.

6.5 Systemic treatments

Chemotherapy, if necessary, will be started at least 3 weeks after surgery with per-operative irradiation.

Hormone therapy will be initiated after surgery and per-operative irradiation.

7-EVALUATION OF EFFICACY

The summary table of investigations is given in annex 1.

PROT ID: 2009/OBS-01

NCT: NCT04414202

Date : 15 Dec 2019

7.1 Primary endpoint

The primary endpoint of this study is the local relapse rate, defined as the number of intra-mammary relapses in the treated breast (regardless of the quadrant and including the skin) and homolateral lymph

relapses in the treated breast (regardless of the quadrant and including the skirl) at

node, assessed at 10 years.

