♥ PATIENT SELECTION	INCLUSION CRITERIA: Women 60 years of age or older, - Histologically proven invasive ductal breast cancer or of a histologically favorable sub-type (mucinous, tubular or colloid), Unifocal tumor, - T1 (diameter ≤ 20 mm), - N0 (pN0 or pNi+), - M0, - Gland exeresis margins ≥ 2 mm, - Estrogen receptor positive, - Information and non-opposition of the patient. EXCLUSION CRITERIA: Inflammatory breast cancer, - Associated peri-tumoral lymphatic - Associated extensive intra-ductal component - Invasive lobular carcinoma - Pure ductal carcinoma in situ, - Sarcoma or lymphoma-type non-epithelial tumor - Synchronous bilateral breast cancer, - Any prior neo-adjuvant treatment: radiotherapy, chemotherapy, hormone therapy	
♥ TREATMENT	The treatment combines extended tumorectomy with axillary dissection (sentinel lymph node) in addition to 20 Gy of peroperative partial irradiation at the tumor site.	
♥ NUMBER OF PATIENTS	The number of patients is based on a recruitment potential of 50 patients per year for 3 years, i.e. 150 patients.	
STATISTICAL ANALYSIS	We seek to demonstrate that the intra-mammary relapse rate is not increased, i.e. a local relapse rate for patients over 60 years of age of between 4 and 7.3% at 10 years.	
♥ STUDY PERIOD	3 years of inclusion. 10 years of follow-up.	

PROT ID: 2009/OBS-01

NCT : NCT04414202 Date : 15 Dec 2019

2- STUDY RATIONALE

Breast carcinoma remains the most common cancer in women in France, where it is currently a major

public health issue, accounting for 37% of new cases of cancer (1).

Its incidence increases considerably and regularly between 30 and 60 years of age, reaching a

maximum plateau (at 320 cases in 100 000) in women 60 to 80 years of age (2).

At the same time, breast cancer mortality has been decreasing since 1980 thanks to the improvement

in treatments along with earlier diagnosis (1).

Therefore, the early pT1N0 stages (diameter ≤ 2 cm without lymph node involvement), which currently

account for 50 to 60% of diagnosed tumors (1), have a specific survival of 88% at 5 years. This

percentage rises to 96% in patients 65 years of age and older (4).

From a therapeutic standpoint, over the past 30 years, many international studies (5-7) have

demonstrated that the combination of breast-conserving surgery and external radiotherapy administered

over the entire breast was equivalent to mastectomy in terms of survival. It has now also been shown

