4.5 End of study evaluation and long-term follow-up

At the end of the 10 years of observation of the study, in compliance with current recommendations, the patients will have annual clinical and radiological monitoring, as usual.

If the patient withdraws or stops the study, the examination will be carried out at the planned date on the follow-up calendar (except for withdrawal from the study for an exceptional reason with conduct of the end of study examination within the 3 days following the withdrawal).

5-PATIENT SELECTION

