7.2 Secondary endpoints

- Study of survival without metastatic relapse, overall survival and specific survival.

- Evaluation of the cosmetic result (annex 4)

- Assessment of the impact of this accelerated treatment on the maintenance of subject's autonomy

using the geriatric scale (ADL, IADL) (annex 3).

-Satisfaction of the patient (annex 4)

8-STATISTIC ANALYSIS

The number of patients is not limited.

However, based on a potential recruitment of 50 patients per year, this study can be analyzed after a

recruitment period of 3 years, or about 150 patients.

The primary assessment will be the rate of intra-mammary relapse, which should remain the same as

after traditional irradiation of the entire breast. This rate of recurrence is estimated in the age series

reported by EORTC (10) between 4 and 7.3% at 10 years for patients over 60 years of age (2 to 3.7%

at 5 years for exponential distribution , with a unilateral confidence interval of 10%). The finding of a

number of relapses 10 / 150 cases at 5 years - during the intermediate analysis - would lead to

questioning this technique.

9- REGULATORY AND ETHICAL ASPECTS

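### The primary endpoint is worded as a number of relapses, with no denominator or rule for incomplete follow-up, yet it is judged against a 10-year time-to-event rate

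*Protocol*

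**What the plan says.** Section 7.1 (Primary endpoint) reads: "The primary endpoint of this study is the local relapse rate, defined as the number of intra-mammary relapses in the treated breast". It adds skin and homolateral node relapse and closes with "node, assessed at 10 years". It states no denominator, time origin or censoring rule.

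The synopsis gives the aim: "We seek to demonstrate that the intra-mammary relapse rate is not increased". Section 8 supplies the yardstick, a rate "reported by EORTC (10) between 4 and 7.3% at 10 years for patients over 60 years of age". It converts this to 2 to 3.7% "at 5 years for exponential distribution , with a unilateral confidence interval of 10" per cent. Its one explicit decision rule is a "number of relapses 10 / 150 cases at 5 years - during the intermediate analysis - would lead to" questioning the technique. Section 8 also says that recruitment is not capped and that about 150 patients are expected in 3 years.

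Follow-up lasts 10 years in women aged 60 or older. Section 4.5 provides for early departure ("If the patient withdraws or stops the study"), but no loss rate is given anywhere.

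**The concern.** A number of relapses is not a rate until it is divided by something. The yardstick is a probability by a fixed time, and halving the time with an exponential model makes sense only on that scale. Endpoint and benchmark are therefore worded on different scales.

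The difference matters as soon as follow-up is incomplete. In a count over all registered patients, a woman lost at year 3 stays in the denominator as relapse-free to year 10, and any later relapse is missed. The figure then moves towards the conclusion the study hopes to reach. The reference range is only 3.3 points wide (7.3 − 4), so a shift of one or two points could change the reading. Without a stated denominator, the choice could also be made after the data are seen.

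**Working it through.** **1. The protocol's own figures.** Exponential conversion from 10 to 5 years is 1 − (1 − p)^0.5. For 4% this gives 2.02% and for 7.3% it gives 3.72%, matching the stated 2 to 3.7%. For the alert count, the binomial probability of at least 10 relapses in 150 at 3.7% is 0.053, and of at least 9 it is 0.106. So 10 is the smallest count at or below a one-sided 10% level. The one-sided 90% exact lower bound is 4.19% for 10/150 (above 3.7%) and 3.65% for 9/150 (below it). These figures are consistent with one another and presuppose that all 150 are followed for 5 years.

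**2. Inputs for the effect of loss.** From the protocol: n = 150, a 10-year horizon, an upper benchmark of 7.3% and exponential relapse times. Assumed: annual loss of 1, 2, 3 or 5%, at a constant hazard and independent of relapse. These equal 10, 18, 26 and 40% lost by 10 years, from 1 − (1 − annual loss)^10.

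**3. Count over all registered patients.** Let λ = −ln(1 − true rate)/10 and μ = −ln(1 − annual loss). The expected crude proportion is λ/(λ+μ) × (1 − exp(−10(λ+μ))).

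Example with a true rate of 10% and 3% annual loss: λ = 0.01054, μ = 0.03046, and the crude proportion is 0.257 × 0.336 = 8.6%.

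Solving for the true rate that reads as a crude 7.3%:

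| Annual loss | True 10-year rate |
|---|---|
| 1% | 7.7% |
| 2% | 8.1% |
| 3% | 8.4% |
| 5% | 9.3% |

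**4. Chance of a falsely reassuring figure.** Take a true rate of 10%. A result counts as inside the range if it is at most 7.3%, which for a crude count means at most 10/150, since 11/150 is 7.33%. The crude column is the binomial probability. The Kaplan-Meier column is a simulation under the same assumptions.

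| Annual loss | Crude | Kaplan-Meier | Excess |
|---|---|---|---|
| none | 11% | 11% | 0 points |
| 1% | 14% | 14% | about 0 points |
| 3% | 24% | 15% | about 9 points |
| 5% | 36% | 17% | about 19 points |

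The excess column is the cost of the crude count. Comparing 24% and 36% with the no-loss 11% would overstate it, because loss also makes a correct estimator less precise.

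**5. The other denominator.** If only relapsed patients and those followed for the full 10 years are counted, the expected figure is crude/(crude + exp(−10(λ+μ))). For a true 7.3% with 10% lost by 10 years this is 0.0693/(0.0693 + 0.8343) = 7.7%. With 20, 30 and 40% lost it is 8.1, 8.7 and 9.3%. The error is now upwards.

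**6. The 5-year rule.** With a true 10-year rate of 12% (6.2% at 5 years), the chance of reaching 10 relapses out of 150 falls from 45% with no loss to 39% if 10% are lost by 5 years and 32% if 20% are lost.

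**The case against.** A reader might infer that the protocol fixes a crude analysis over all registered patients, and that any loss must then favour the technique. The text does not go that far.

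- Section 7.1 names no denominator. Its main work is to list which events count. A relapse rate at 10 years is compatible with Kaplan-Meier or cumulative incidence, and an analysis plan that is not shown may specify one. The exponential conversion in section 8 even suggests time-to-event thinking. This stands. However, the endpoint definition itself sits in the protocol, is worded as a number, and the only worked rule uses a fixed 150.
- The downward direction holds only for the all-patients denominator and reverses for completers. Section 7.1 also counts homolateral node relapse while the section 8 benchmark is intra-mammary only, which pushes the figure up. The net direction is therefore not certain. This stands.
- The loss rates are assumptions. Section 4.5 speaks of withdrawal only conditionally, and 5% per year would mean 40% lost at a single centre with routine annual follow-up. This stands. At 1% per year the practical harm is negligible.
- The protocol does not say how the cited series estimated its rate. A competing-risk estimate lies below 1 minus Kaplan-Meier when patients die without relapse, so imposing it alone could create a fresh mismatch. This stands and shapes the fix.

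**Conclusion.** The point holds as a defect of definition. The primary endpoint is a number with no denominator or rule for incomplete follow-up, set against a 10-year probability, and the companion 5-year rule is a raw count over a fixed 150. On the reading that this rule supports, the reported figure is too low by about 0.4 points at 1% annual loss (7.7 − 7.3) and 2.0 points at 5% (9.3 − 7.3). With a true rate of 10%, the added chance of a reassuring result is about 0 to 19 points. These sizes rest on constant hazards, loss independent of relapse, 150 patients and loss rates that the protocol does not give. A completers-only reading gives an error of similar size in the other direction. The documents do not establish that a biased analysis will be done. They leave room for one in either direction. The change is worth making, with moderate confidence in its practical weight.

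**What to change.** In sections 7.1 and 8:

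- Define the primary endpoint as the 10-year probability of local relapse, measured from surgery, with patients not known to have relapsed or died censored at their last breast assessment.
- Estimate it by cumulative incidence with death without relapse as a competing event, and also report 1 minus Kaplan-Meier. For the comparison with 4 to 7.3%, use whichever estimator the cited series used, and say which that is.
- Report the one-sided 90% confidence bound, in line with the 10% level in section 8.
- Express the 5-year rule on the same scale, for example as the one-sided 90% lower bound of the 5-year estimate compared with 3.7%. With complete follow-up of 150 patients and exact bounds this reproduces the present count of 10.

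The cost is wording. The scheduled clinical visits and annual imaging should supply the dates, so no extra examination is needed. Compared with a raw count over all patients, the reported figure will be slightly less favourable and slightly less simple to explain.

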 	RATIONALE	Due to screening, T1N0 early-stage breast cancer now accounts for more than 50% of the tumors diagnosed in France. The prognosis of these tumors is good, even excellent in women ≥ 65 years of age, with specific survival of 98% at 5 years. The treatment of these tumors most often combines breast-conserving surgery and external whole breast irradiation for 6.5 weeks. A true de-escalation of treatment is taking place with these tumors, both surgically and medically. Surgery therefore now prefers breast-conserving methods in combination with exeresis of the sentinel lymph node only. In the same way, in many international studies, radiotherapy has been evaluating the possibility of reducing both: - the irradiation volume at the excision site (partial irradiation) - the duration of this irradiation (accelerated radiotherapy) Between 2004 and 2007, the CRLC [Regional Anti-Cancer Center] thus evaluated the feasibility and the oncological results of intra-operative partial irradiation via a phase II study in women 65 years of age and older with T1N0M0 hormonesensitive tumors with a good prognosis. From 2010 to 2013, the ICM carried out an observational study of these tumors with an excellent prognosis. In July 2009, the American Society for Radiation Oncology (ASTRO) published a consensus statement with specific recommendations and indications for accelerated partial breast irradiation (APBI). This APBI technique has been developing in France over the past 5 years within the framework of clinical studies and in compliance with the 2012 recommendations of the French National Cancer Institute. This APBI can be given by 3D external radiotherapy or, as in this study, by intra-operative radiotherapy (IORT) in order to obtain optimal precision and spare as much of the surrounding healthy tissue as possible.

PROTOCOLE INTRA OBS PROT ID: 2009/OBS-01 NCT: NCT04414202 Date: 15 Dec 2019

Date : 10 Dec 2019		
	We therefore propose a cohort study to prospectively analyze the results of this technique applied to the indications strictly defined by the ASTRO.	
	Primary: Local intra-mammary relapse rate	
♦ OBJECTIVES	Secondary: - Cosmetic results - Survival without metastatic relapse - Satisfaction of the patient with regard to her treatment - Impact of the accelerated treatment on the maintenance of autonomy in elderly patients	

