3.1 Primary objective

To evaluate the local relapse rate after local treatment combining extended tumorectomy with axillary

(sentinel lymph node) dissection and per-operative partial irradiation of the tumor bed.

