4.4 Follow-up evaluation during the study

The follow-up of patients treated in the study is conventional monitoring in compliance with the current recommendations.

It will be based on a physical examination every semester for the first 5 years. This clinical follow-up will then be carried out annually from the 6th to the 10th year.

The para-clinical examinations will be limited to annual mammography and breast ultrasound. Breast MRI remains optional. In case of suspected local relapse (clinical and/or radiological), histological confirmation will be obtained.

The evaluation of autonomy (ADL and IADL) (annex 3) as well as the patient satisfaction index (annex 4) will be evaluated at 3 weeks, 6 months and 12 months of treatment to assess its impact.

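### Two primary events: section 7.1 counts breast plus homolateral nodal relapse, while the synopsis and section 8 count intra-mammary relapse only

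*Protocol*

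**What the plan says.** Section 7.1 defines the local relapse rate, the primary endpoint, as "defined as the number of intra-mammary relapses in the treated breast (regardless of the quadrant and including the skin) and homolateral lymph" "node, assessed at 10 years". A line is repeated in the middle of this sentence in the available text, but the two halves plainly read as homolateral lymph node.

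Three other places name the breast alone:

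- Synopsis, Objectives: "Primary: Local intra-mammary relapse rate".
- Synopsis, Statistical analysis: "We seek to demonstrate that the intra-mammary relapse rate is not increased".
- Section 8: "The primary assessment will be the rate of intra-mammary relapse, which should remain the same as" after conventional whole-breast irradiation.

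Section 3.1 is neutral: "To evaluate the local relapse rate after local treatment combining extended tumorectomy with axillary" dissection, with no site of relapse named. Section 7.2 does not list nodal relapse as a secondary endpoint.

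Section 8 attaches to the intra-mammary rate a benchmark of 4 to 7.3% at 10 years, converted to 2 to 3.7% at 5 years under an exponential model, with a one-sided 10% level. It adds that 10 relapses in 150 patients at 5 years would call the technique into question.

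**The concern.** This is a single cohort judged only against an external rate, and about ten events decide the signal. The definition of the event therefore carries the whole primary result, and the protocol gives two.

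An analyst who follows section 8 compares like with like, as the protocol presents its benchmark, but does not analyse the endpoint defined in 7.1. An analyst who carries 7.1 into section 8 counts nodal relapses towards a threshold set without them. On the protocol's own account of the benchmark, that tilts the comparison against the technique. While the matter stays open, the choice could be made after the relapses and their sites are known.

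**Working it through.** **Inputs from section 8.** n = 150; benchmark 4 to 7.3% at 10 years; exponential model; one-sided 10%; alert at 10 relapses at 5 years. Complete follow-up is assumed, so the count X is binomial.

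**Step 1: reproduce the 5-year benchmark.** Under an exponential model, p5 = 1 − √(1 − p10).

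- 1 − √(1 − 0.040) = 2.02%
- 1 − √(1 − 0.073) = 3.72%

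Both match the stated 2 to 3.7%.

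**Step 2: reproduce the alert.** With X ~ Binomial(150, 0.037):

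- P(X ≥ 9) = 10.6%, above 10%
- P(X ≥ 10) = 5.3%, below 10%

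Ten is the smallest count that meets the one-sided 10% level. The exact one-sided 90% lower confidence limit agrees: 3.65% for 9/150 (below 3.7%) and 4.19% for 10/150 (above it). The alert is thus set to the 3.7% ceiling that section 8 ties to intra-mammary relapse, with no allowance for nodal events.

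**Step 3: same data, two readings.** Take 8 breast-only and 2 node-only relapses in 150 patients. Section 7.1 counts 8 + 2 = 10, and the alert is reached. Section 8 counts 8, and it is not.

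**Step 4: size of the effect.** The protocol gives no nodal rate, so the added points below are assumptions, first without overlap with breast relapse. The entries are P(X ≥ 10) with p = breast rate + added points. The middle row is the midpoint, (2 + 3.7)/2 = 2.85%.

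| 5-year breast rate | +0 | +0.5 | +1 | +2 points |
|---|---|---|---|---|
| 3.7% | 5.3% | 10.2% | 17.0% | 35.2% |
| 2.85% | 1.1% | 3.0% | 6.5% | 19.4% |
| 2% | 0.1% | 0.5% | 1.6% | 8.0% |

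P(X ≥ 10) reaches 10% at p = 4.19%. The nodal addition needed to get there is 4.19 − 3.7 ≈ 0.5 points, 4.19 − 2.85 ≈ 1.3 points, or 4.19 − 2 ≈ 2.2 points.

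If half of the nodal relapses occur in patients who also relapse in the breast, the additions halve to 0.25, 0.5 and 1 point. The 3.7% row then reads 7.5%, 10.2% and 17.0%.

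**Step 5: threshold for the combined event.** Smallest count with a one-sided probability of at most 10% against the ceiling plus the assumed nodal rate:

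- 3.7 + 0.5 = 4.2%: 11 (5.2%)
- 3.7 + 1 = 4.7%: 11 (9.7%)
- 3.7 + 2 = 5.7%: 13 (8.8%)

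**The case against.** The strongest case on the other side is that the protocol uses its terms loosely rather than holding two endpoints. The synopsis statistical sentence, read further, equates the two labels: "We seek to demonstrate that the intra-mammary relapse rate is not increased, i.e. a local relapse rate for patients over 60 years of age". It attaches the 4 to 7.3% range to the second label. The alert sentence in section 8 speaks only of relapses, without a site. Section 2, citing the same source, speaks of local relapse. What that source counted cannot be seen here. The nodal rates above are assumptions, and the largest, 2 points, equals the whole lower benchmark. At breast rates of 2% or 2.85%, adding 0.5 or 1 point leaves the alert probability below 10%, and in two of the three scenarios the re-derived threshold moves by one event. The alert is also worded as a prompt to question the technique, not as a formal stopping rule.

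Much of this stands as a limit on the size of the effect. The intra-mammary meaning of the alert is inferred from the sentences before it and from its calibration to 3.7%. The direction of bias holds only if the benchmark counts what section 8 says it counts. None of it removes the contradiction. Section 7.1 adds nodal relapse expressly, and section 8 names the breast. The unqualified wording of the alert makes matters worse, because a reader coming from 7.1 would count nodes there.

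**Conclusion.** The concern holds and must be fixed. The primary event is defined in two incompatible ways, and an analysis plan could follow one passage only by departing from another. That conclusion needs no assumption.

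The numerical effect does need assumptions: n = 150, complete follow-up and an unknown nodal rate. It ranges from negligible (2% breast rate with 0.5 added points: 0.1% to 0.5%) to large (3.7% with 2 added points: 5.3% to 35.2%). At the ceiling, about half a percentage point of additional nodal relapse is enough to pass the 10% level. The arithmetic of section 8 is sound for an intra-mammary event.

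**What to change.** Choose one event, without knowledge of outcomes, and use it everywhere.

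**Preferred.** In 7.1, define the primary event as intra-mammary relapse in the treated breast, in any quadrant and including the skin. This matches the synopsis, section 8 and the benchmark as the protocol presents it. Say in 3.1 and section 8 that the event, including the count of 10 in 150, is intra-mammary relapse. Add homolateral nodal relapse and the combined loco-regional rate to 7.2. The downside is that nodal events leave the formal primary endpoint.

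**Alternative.** Keep the combined event of 7.1, state it in 3.1, change the synopsis and section 8 to match, and re-derive the benchmark and the alert count. Under the assumptions above, the count would be 11, 11 or 13 instead of 10. The downside is that this needs a benchmark for the combined event, which the protocol does not give.

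Either way the cost is wording, with no change in sample size or visits. The site of each relapse (breast or node) must be recorded. Section 4.4 says only "In case of suspected local relapse (clinical and/or radiological), histological confirmation will be obtained", so the recording of site should be stated there.
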